## 10.1 Main analysis

Due to the observational nature of the study, all analyses are exploratory. No weighting will be applied to either of the co-primary endpoints.

For the analysis of the primary outcomes

- Correlation between change from baseline to week 52 in FVC [% pred.] and change from baseline to week 52 in dyspnea symptom score
- Correlation between change from baseline to week 52 in FVC [% pred.] and change from baseline to week 52 in cough symptom score

Pearson measures of correlation along with 95% two-sided confidence intervals and the two-sided p-values will be provided.

For the secondary outcomes

[figure not shown]
- Correlation between change from baseline to week 52 in FVC [mL] and change from baseline to week 52 in dyspnea symptom score
- Correlation between change from baseline to week 52 in FVC [mL] and change from baseline to week 52 in cough symptom score

Pearson measures of correlation along with 95% two-sided confidence intervals and the two-sided p-values will be provided.

The secondary outcomes

- absolute change from baseline in L-PF symptoms dyspnoea domain score between week 52 and baseline
- absolute change from baseline in L-PF symptoms cough domain score between week 52 and baseline

will be analyzed using a restricted maximum likelihood (REML) based repeated measures approach. Analyses will include the fixed, categorical effect of visit, as well as the continuous, fixed covariates of baseline and baseline-by-visit interaction. An unstructured (co)variance structure will be used to model the within-patient measurements.

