Parameter	Visit 1; baseline visit	Visit 2; (optional) ca. week 13	Visit 3; mid of observation; ca. week 26*	Visit 4; (optional) ca. week 39	Visit 5; end of observation; ca. week 52	Visit 6 FU ca. week 52**	
Rationale for treatment discontinuation (if applicable)		X	X	X	X		
Further treatment options yes/no (as applicable)		X	X	X	X	X	
Intention to continue or discontinue treatment with nintedanib after the study (yes/no)		X	X	X	X		
Survival data							X

\* after 26 weeks of observation for each individual patient  
\*\* if available and/or patients is willing to perform, phone contact acceptable

In addition to the mandatory visits, i.e. Visit 1 (baseline), Visit 3 (mid of observation; 26 weeks after baseline) and Visit 5 (end of observation) and Visit 6 (Follow-up 52 weeks after baseline), optional study visits will be enabled between V1 and V3 (V2) as well as between V3 and V5 (V4), each occurring about midway between V1 and V3 or V3 and V5, respectively. Therefore, patients will be seen by their study investigator at least every 6 months and up to every quarter of the observational period.

When optional visits are conducted, then the same parameters as in Visit 3 should be documented.

Each visit should take place not earlier than six weeks before and no later than six weeks after the planned visit date and thus reflect patients' and physicians' real-world experience.

Survival data are to be collected 52 weeks after inclusion for all patients - including those patients who drop out. Patients who discontinue the study before week 52 for any reason should be contacted for survival status and follow-up data at week 52 (visit 6). For all other patients, visit 5 and visit 6 are completed in the same visit.

Name of company: Boehringer Ingelheim																					
Name of finished medicinal product: Ofev®																					
Name of active ingredient: L01XE31 Nintedanib																					
Protocol date: 15-Dec-2020	Study number: 1199-0449	Version/Revision: 2.0	Version/Revision date: 8-Feb-2021																		

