### 5.2 SECONDARY OBJECTIVE

- Correlation between change from baseline to week 52 in FVC [mL] and change from baseline to week 52 in dyspnea symptom score
- Correlation between change from baseline to week 52 in FVC [mL] and change from baseline to week 52 in cough symptom score
- Absolute change from baseline in L-PF cough symptom score at week 52
- Absolute change from baseline in L-PF dyspnea symptom score at week 52

Primary and secondary objectives will be analyzed for the Treated Set.

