## 6. RESEARCH METHODS

### 6.1 STUDY DESIGN

This is a single-arm, open-label observational cohort study according to §4, section 23 and §67, section 6 German Medicines Act (NIS): All included chronic fibrosing ILD with a progressive phenotype patients will receive treatment with nintedanib for approximately 52 weeks. NIS based on newly collected data.

For more details on study design please see section 9.1 of the Study Protocol.

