**9.2.1 Change from baseline endpoints**

The statistical Mixed effect Model for Repeated Measures (MMRM) used for the analysis of continuous secondary endpoints allows for form-level missing data, assuming they are missing at random. Item-level data for the PRO measures will be handled according to the instructions provided by the instrument developer.

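### SAP 10.1 does not say what the single-arm week-52 mean L-PF change estimates or at which baseline it is read off; the usual model-based SE would be somewhat too small for the population mean change

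*SAP*

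**What the plan says.** SAP 6.1 states the design: "This is a single-arm, open-label observational cohort study". SAP 5.2 lists among the secondary objectives "Absolute change from baseline in L-PF dyspnea symptom score at week 52", with a parallel entry for cough.

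SAP 10.1 says that these two outcomes "will be analyzed using a restricted maximum likelihood (REML) based repeated measures approach". It continues: "Analyses will include the fixed, categorical effect of visit, as well as the continuous, fixed covariates of baseline and baseline-by-visit interaction", and "An unstructured (co)variance structure will be used to model the within-patient measurements". Protocol 9.7.1 has the same text.

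The sentence on intervals, "Pearson measures of correlation along with 95% two-sided confidence intervals and the two-sided p-values will be provided", is attached to the correlation outcomes. For the repeated-measures model the section mentions no SE, no CI, no adjusted mean and no baseline value for evaluation.

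The number of records per patient will vary. Protocol section 4 says that "optional study visits will be enabled between V1 and V3 (V2) as well as between V3 and V5 (V4"), and SAP 9.2.1 says that the model "allows for form-level missing data, assuming they are missing at random". SAP section 10 restricts the main analysis to visits inside the time windows and to patients with available data. SAP Annex 1 places the table shells in a separate technical document, which is not part of the material reviewed here.

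**The concern.** A model with baseline and baseline-by-visit terms suits a comparison of two arms, because the baseline value at which adjusted means are computed drops out of the difference. Here nothing drops out. The week-52 mean change is the visit effect plus the week-52 slope times whatever baseline value is chosen.

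Two things follow. An adjusted mean evaluated at the sample baseline mean, with the ordinary model-based SE, ignores the sampling error of that mean. And when patients contribute different numbers of records, or none, there are several candidate baseline means: all treated patients, patients with any follow-up, all analysed records, or week-52 completers. They need not agree.

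There is no control arm, and Protocol section 7 looks to these changes for evidence on whether nintedanib acts directly on patient-reported outcomes. The estimate and its error bars are all that the reader will have.

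**Working it through.** **Inputs.** From the documents: one arm, the model terms above, N = 84 evaluable and 100 recruited with about 15% dropout (Protocol 9.5). The documents give no L-PF SD, no baseline/week-52 correlation, and no SE or CI width for these outcomes. The correlation r and the SD ratio k (week-52 SD divided by baseline SD) are therefore assumptions, shown as ranges.

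**The plan's own figure.** N = 84 belongs to the primary correlation. Fisher z gives ((1.960 + 0.842)/atanh(0.3))² + 3 = 84.9; a bias-corrected version gives 83.98, i.e. 84; simulated power at 84 is 80.1%. With 15% dropout, 84/0.85 = 98.8, i.e. 99, in line with 100. The figure reproduces and is not affected by this point.

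**SE with complete data.** Let d be the change, b the baseline and β the slope of d on b. The adjusted mean at the sample mean of b equals the plain mean of d.
- Model variance: Var(d) × (1 − R²)/n.
- Sampling variance for the population mean change: Var(d)/n.
- Omitted part: R² × Var(d)/n = β² × Var(b)/n.
- SE ratio: √(1 − R²).

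In units of the baseline SD, β = rk − 1, Var(d) = 1 + k² − 2rk and R² = β²/Var(d). With k = 1 this is R² = (1 − r)/2.

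Coverage below is from 40,000 simulated trials per setting (n = 84 and n = 100, k = 1):

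| r | R² | SE ratio | Coverage, model SE | Coverage, paired SE |
|---|---|---|---|---|
| 0.9 | 0.05 | 0.975 | 94.4% | 95.0–95.1% |
| 0.8 | 0.10 | 0.949 | 93.8–93.9% | 95.1% |
| 0.7 | 0.15 | 0.922 | 93.0–93.1% | 95.0–95.1% |
| 0.6 | 0.20 | 0.894 | 92.0–92.2% | 94.9–95.0% |
| 0.5 | 0.25 | 0.866 | 91.1% | 95.0–95.1% |

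Against a different target, the mean change at the realised baseline mean, the same model interval covers 94.9% to 95.1%.

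**Sensitivity to k.**
- k = 1.15: r = 0.7 gives β = −0.195, Var(d) = 0.7125, R² = 0.053, ratio 0.973, coverage 94.4%. At r = 0.8 the ratio is 0.993 (94.9%). At r = 0.5 it is still 0.920 (92.9%).
- k = 0.9, r = 0.7: β = −0.37, Var(d) = 0.55, R² = 0.249, ratio 0.867.

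**Repeated-measures check.** Unstructured REML, 100 patients, optional visits, 15% dropout, 150 runs per setting. This is rough: the relative error of an empirical SE is about 1/√300 = 6%. Evaluated at the all-treated baseline mean, in baseline-SD units:

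| Setting | β | Model SE | Empirical SE | √(model SE² + β²/100) |
|---|---|---|---|---|
| r = 0.5, missingness unrelated to baseline | −0.50 | 0.0932 | 0.1059 | 0.1058 |
| r = 0.7, missingness unrelated to baseline | −0.31 | 0.0767 | 0.0858 | 0.0827 |
| r = 0.7, visits and dropout related to baseline | −0.31 | 0.0770 | 0.0799 | 0.0830 |

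Over all four candidate baseline means, model SE divided by empirical SE was 0.86–0.90 in the first two settings and 0.93–0.96 in the third. Adding the omitted term brings the SE to within simulation error of the empirical value.

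**Which baseline mean.** A patient seen at V2 to V5 has four post-baseline records against two for one seen only at V3 and V5, so counts twice in a record-weighted mean. Record-weighted against all-treated evaluation moved the estimate by 0.13 to 0.17 SE on average in absolute terms; the mean signed shift was between −0.006 and 0.001. In the third setting, evaluating at the week-52 completers' mean gave 0.237 against 0.202 for the all-treated mean (true value 0.20): (0.237 − 0.202)/0.0770 = 0.45 SE. That shift comes from baseline-dependent dropout, not from optional visits.

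**The case against.** A reader might infer that the plan lays down a confidence interval that under-covers. The documents do not support that. SAP 10.1 ties its 95% intervals to the correlations, and evaluation at the sample baseline mean is an inference from the model terms. The technical document named in Annex 1 might settle both the evaluation point and the interval. The inference is a natural one, since the INBUILD changes in the Protocol's study-size section are labelled as adjusted means with SE, but it remains an inference.

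The shortfall also depends on the target. For the mean change at the realised baseline mean the model interval is correct, and the SAP does not say which target it means. Nor does any document supply r or k; if L-PF scores spread out over the year, almost nothing may be lost.

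Finally, a baseline-adjusted model is not an error in itself, SAP section 10 openly limits the analysis to patients with available data, and all analyses are exploratory. No power statement or decision threshold rests on these intervals, and the Protocol itself warns that uncontrolled change is hard to interpret. All of this stands and limits the point to a minor one. It does not remove it: the target and evaluation point are open, and for the population mean change the usual output would be too precise.

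**Conclusion.** The point holds in a conditional form. If the week-52 mean is read off at the sample baseline mean with its model-based SE, and the target is the population mean change, the SE is about 2.5% to 13% too small and coverage is about 94.4% down to 91%. This assumes equal SDs and correlations from 0.9 to 0.5. The shortfall is larger if the week-52 SD is below the baseline SD, and close to nil if it is about 1.15 times baseline at correlations of 0.7 or more.

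The estimate also depends modestly on which baseline mean is used, by about 0.13 to 0.17 SE for record-weighted against all-treated. A reader might go further and conclude that the result describes those who attended optional visits and not the treated set. That would need a record-averaged evaluation, attendance that rises with symptoms, a sizeable slope and an assumed SD, none of which the documents give.

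The primary correlations and N = 84 are unaffected. Severity is minor.

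**What to change.** In SAP 10.1, state that the target is the mean change in the treated population. Model the L-PF score at V1 to V5 as the response, with visit as the only fixed effect, unstructured covariance and REML, and report the V5 minus V1 contrast with its 95% CI. This keeps the missing-at-random assumption, uses every available treated-set baseline, and gives essentially the same point estimate as the present model evaluated at the treated-set mean baseline. It also needs no choice of evaluation point.

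Alternatively, keep the present model, evaluate it at the treated-set mean baseline (one record per patient), and add slope² × Var(baseline)/n to the variance, where n is the number of patients in that mean.

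The cost is one changed model statement. Intervals become up to about 15% wider (1/0.866 = 1.155 at r = 0.5 with equal SDs). The first option has two more parameters: 5 visit means + 15 covariance terms = 20, against 8 fixed effects + 10 covariance terms = 18.

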### 10.3 Safety Analysis

All adverse drug reactions (ADRs) (serious and non-serious) and all AEs with fatal outcome as collected per study protocol will be included and summarized in the final study report. Separate tables will be provided for patients with serious adverse events.

Adverse events will be coded using the Medical Dictionary for Regulatory Activities (MedDRA) coding dictionary. Standard BI summary tables and listings will be produced. All treated patients will be included in the safety analysis. In general, safety analyses will be descriptive in nature and will be based on BI standards. All analyses will be based on the number of patients with AEs and not on the number of events. No hypothesis testing is planned.

Kaplan-Meier plots will be produced for the time to premature treatment discontinuation, for the time to first dose reduction and for the time to first treatment interruption.

Statistical analysis and reporting of adverse events will concentrate on treatment-emergent adverse events (TEAE).

Frequency, severity, and causal relationship of adverse events will be tabulated by system organ class (SOC) and preferred term (PT) after coding according to the current version of MedDRA.

Adverse events relating to gastrointestinal perforation and hepatic injury will be considered as adverse event of special interest (AESI) and will be tabulated separately.

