So, the time needed by the patient for the whole study depends on the number of visits performed. The duration of each visit depends on the amount of data to be collected and the possible questions to be discussed between investigator and participant. For baseline, we

presume about one hour, for the following visits about 30 minutes including filling out the questionnaire.

All details on the data collected and tasks performed at each visit are shown in [table 9.2.3: 1](#).

Table 9.2.3: 1 Flow Chart

Parameter	Visit 1; baseline visit	Visit 2; (optional) ca. week 13	Visit 3; mid of observa- tion; ca. week 26*	Visit 4; (optional) ca. week 39	Visit 5; end of observa- tion; ca. week 52	Visit 6 FU ca. week 52**
Informed Consent	X					
Inclusion / Exclusion Criteria	X					
Patient demographics (age, gender, height, and weight)	X					
Smoking history	X					
History of ILD, including ILD entity and HRCT pattern (where available in patient documentation)		X				
current DLCO measures (where available in patient documentation)	X	X	X	X	X	
Concomitant diseases / Comorbidities	X	X	X	X	X	
Past ILD therapies (6 weeks before visit 1)	X					
Current ILD related or other relevant concomitant medication	X	X	X	X	X	
FVC (mL and % pred.; if available in patient data)	X	X	X	X	X	X
Severity of disease as per the treating physician's estimation (if available in patient data)	X	X	X	X	X	X
L-PF questionnaire, completed by patient	X	X	X	X	X	X

Table 9.2.3: 1 (cont'd)

Flow Chart

Parameter	Visit 1; baseline visit	Visit 2; (optional) ca. week 13	Visit 3; mid of observa- tion; ca. week 26*	Visit 4; (optional) ca. week 39	Visit 5; end of observa- tion; ca. week 52	Visit 6 FU ca. week 52**
Safety: Adverse Drug Reactions (serious and non-serious), fatal AEs, pregnancy	X	X	X	X	X	X
Rationale for treatment discontinuation (if applicable)		X	X	X	X	
Further treatment options yes/no (as applicable)		X	X	X	X	X
Intention to continue or discontinue treatment with nintedanib after the study (yes/no)		X	X	X	X	
Survival data						X

\* after 26 weeks of observation for each individual patient

\*\* if available and/or patients willing to perform, phone contact acceptable

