## 11.2 ADVERSE EVENT AND SERIOUS ADVERSE EVENT COLLECTION AND REPORTING

The investigator shall maintain and keep detailed records of all AEs in their patient files.

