**Pregnancy:**

In rare cases, pregnancy might occur in a NIS. Once a patient has been enrolled in the study and has taken study medication, the investigator must report any drug exposure during pregnancy in a study participant within 7 days by means of Part A of the Pregnancy Monitoring Form to the sponsor's unique entry point.

The outcome of the pregnancy associated with the drug exposure during pregnancy must be followed up and reported to the sponsor's unique entry point on the Pregnancy Monitoring Form (Part B).

The ISF will contain the Pregnancy Monitoring Form (Part A and B). As pregnancy itself is not to be reported as an AE, in the absence of an accompanying serious ADR and/or AESI, only the Pregnancy Monitoring Form and not the NIS AE form is to be completed. If there is a serious ADR and/or AESI associated with the pregnancy a NIS AE form must be completed in addition.

The following must be collected by the investigator in the (e)CRF from signing the informed consent onwards until the end of the study:

all adverse drug reactions (ADRs) (serious and non-serious),  
all AEs with fatal outcome,  
all AESIs

All ADRs and AESIs, including those persisting after study completion must be followed up until they are resolved, have been sufficiently characterized, or no further information can be obtained.

Expedited Reporting of AEs and Drug Exposure during Pregnancy to BI Pharmacovigilance

The following must be reported by the investigator on the NIS AE form and/or Pregnancy Monitoring Form from signing the informed consent onwards until the end of the study and provide o BI unique entry point:

All serious ADRs associated with the studied medical product nintedanib	immediately within 24 hours
All AEs with fatal outcome in patients exposed to studied medical product nintedanib	immediately within 24 hours
All protocol specified AESIs	Immediately within 24 hours
All non-serious ADRs associated with the studied medical product nintedanib	7 calendar days
Drug exposure during pregnancy	7 calendar days

The same timelines apply if follow-up information becomes available for the respective events. In specific occasions the Investigator could inform the Sponsor upfront via telephone. This does not replace the requirement to complete and fax the NIS AE form.

Information required

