## 7. VARIABLES

The following parameters will be collected and assessed at visits 1 to 5, as applicable:

- Patient demographics (age, gender, height, weight)
- Smoking history, current status (current smokers, former smokers, and never smokers) and pack-years
- History of ILD, including ILD entity and HRCT pattern (where available in patient documentation)
- current DLCO measures (where available in patient documentation)
- Concomitant diseases
- Previous ILD therapies in the 6 weeks before visit 1
- Current ILD related or other relevant concomitant medication
- FVC (mL and % pred.; if available in patient data)
- Severity of disease as per the treating physician's estimation (if available in patient data)
- L-PF questionnaire, completed by patient
- Safety: ADRs (serious and non-serious), fatal AEs, pregnancies during the study
- Rationale for treatment discontinuation (if applicable)
- Intention to continue or discontinue treatment with nintedanib (Ofev®) after the study (yes/no)
- Further treatment options yes/no, as applicable

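### The planned SAE, treatment-emergent AE and causality tables are labelled more widely than the events the study collects

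*SAP*

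**What the plan says.** **Collection.** Protocol 11.2 introduces the eCRF safety data with "The following must be collected by the investigator in the (e)CRF from signing the informed consent onwards until the end of the study". Three categories follow: adverse drug reactions of any seriousness, "all AEs with fatal outcome", and all AESIs. The flow chart in Protocol 9.2.3 has one safety row, "Safety: Adverse Drug Reactions (serious and non-serious), fatal AEs, pregnancy", and SAP 7 lists "Safety: ADRs (serious and non-serious), fatal AEs, pregnancies during the study". Neither names AESIs, and neither has an entry for all AEs or all SAEs. Other events stay at the site: "The investigator shall maintain and keep detailed records of all AEs in their patient files" (Protocol 11.2).

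**Definitions.** In Protocol 11.1 an AE counts whether or not it is thought related to the product, and an SAE is any AE that meets a seriousness criterion, hospitalisation among them. An ADR requires at least a reasonable possibility of a causal link. AESIs (gastrointestinal perforation and hepatic injury) carry no causality condition.

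**Analysis.** SAP 10.3 opens by saying that the ADRs and fatal AEs collected under the protocol will be summarised. The next sentence is "Separate tables will be provided for patients with serious adverse events". The section then concentrates on treatment-emergent AEs, tabulates frequency, severity and causal relationship by organ class and preferred term, and plans a separate AESI table. Counts are of patients, not events. SAP 10 expresses percentages relative to the treated set. The SAE-table sentence has no counterpart in Protocol 9.7.3.

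**The concern.** The table titles use the terms SAE and AE, which the protocol defines without regard to causality. The database, for the most part, holds events selected because they were judged related. A patient admitted to hospital for something unrelated who survives, with no AESI, has had an SAE as the protocol defines it. That event is not among the items collected, so the patient is not counted for it.

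The output would be a number and percentage of treated patients with SAEs, which a reader of the report would naturally take as an SAE incidence. It would be too low whenever at least one patient's only SAEs are of the uncollected kind, and it would err in the direction that flatters the drug. The causality table has the opposite problem: because unrelated events are mostly filtered out at entry, a high related share partly reflects the collection rule. No primary or secondary result is affected. What is at stake is what the safety section can be read to show.

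**Working it through.** The plan states no SAE rate or relatedness share, so there is no figure to reproduce. The check is first textual, then illustrative.

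**Step 1: which serious events reach the database.** This applies the definitions in Protocol 11.1 to the list in Protocol 11.2.

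| Serious event | SAE by Protocol 11.1? | Entered in eCRF? |
|---|---|---|
| Judged related, any outcome | Yes | Yes, as an ADR |
| Unrelated, fatal | Yes | Yes, as a fatal AE |
| Unrelated, non-fatal, AESI | Yes | Yes, as an AESI |
| Unrelated, non-fatal, not an AESI | Yes | No |

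The same filter applies to non-serious events: an unrelated one is entered only if it is an AESI. The treatment-emergent AE definition in SAP 7 starts from all adverse events in the time window, and the database cannot supply that set.

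**Step 2: causality among collected events.** An event that is neither fatal nor an AESI can enter only as an ADR, so it is related by definition. Fatal AEs and AESIs enter whatever their causality. Only for these does the causality column carry information.

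**Step 3: illustrative size.** All three inputs are assumptions; none comes from the documents.

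- r, share of SAEs judged related: 10% to 50%
- f, share of unrelated SAEs that are fatal: 5% to 25%
- a, share of unrelated SAEs that are non-fatal AESIs: 2%

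Share captured = r + (1 − r)(f + a). Share missed = (1 − r)(1 − f − a). Related share among captured SAEs = r / share captured.

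- Most missed (r = 0.10, f = 0.05): captured 0.10 + 0.90 × 0.07 = 0.163; missed 0.837.
- Least missed (r = 0.50, f = 0.25): captured 0.50 + 0.50 × 0.27 = 0.635; missed 0.365.
- Middle case (r = 0.30, f = 0.15): captured 0.30 + 0.70 × 0.17 = 0.419; missed 0.581. With 100 treated patients, 30 of whom have one SAE each, about 30 × 0.419 = 12.6 are captured. The table would show about 12.6% in place of 30%.

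The related share shown would be 0.30 / 0.419 = 72% in the middle case, against an assumed true 30%. Over the grid it runs from 0.10 / 0.343 = 29% (r = 0.10, f = 0.25; true 10%) to 0.50 / 0.535 = 93% (r = 0.50, f = 0.05; true 50%).

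The formula counts events, while SAP 10.3 counts patients. The two agree when each patient has at most one SAE. A patient with several is counted if any one of them was collected, so the shortfall in patients would then be smaller.

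**The case against.** The best defence is that the scope is already stated. The sentence just before the SAE-table sentence limits the summary to ADRs and fatal AEs as collected, so the SAE tables can be read as the serious subset of those events. Selective collection is an open design choice in a non-interventional study that is not a PASS, safety is descriptive with no testing, and counts of the collected events would be correct. The shells sit in a separate technical SAP (SAP Annex 1), which may already carry suitable titles or footnotes and cannot be checked here.

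Much of this stands. The collection rule itself is not at fault, and the defect lies in labelling and interpretation. But the limiting phrase belongs to the sentence on ADRs and fatal AEs and is not attached to the SAE, treatment-emergent AE or causality tables. SAP text also does not travel with a table into a report. If the shells already state the scope, the remaining change is small.

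Two stronger readings are tempting. A reader might infer that every event in the causality table will be related. That is not so, because fatal AEs and AESIs are collected regardless of causality. A reader might also infer that a safety comparison with INBUILD is planned and would be distorted. The documents plan none: Protocol 9.9 compares baseline characteristics only, and Protocol 7 says just that the data will complement INBUILD.

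**Conclusion.** The point holds as a mismatch between what is collected and how the tables are labelled. The SAE and treatment-emergent AE percentages in SAP 10.3 will leave out all unrelated events that are neither fatal nor AESIs, so they are not incidences under the protocol's definitions. Causality is fixed as related for events that are neither fatal nor AESIs, and the overall tabulation is shifted that way without being wholly related.

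The direction is certain; the size cannot be derived from the documents. Under the stated assumptions (10-50% of SAEs related, 5-25% of unrelated SAEs fatal, 2% of unrelated SAEs non-fatal AESIs), between 36% and 84% of SAEs would be missed. A reader might infer that the missed share is simply one minus the related share. That overstates it, because unrelated fatal SAEs and unrelated AESIs are collected and would appear in the tables.

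**What to change.** In SAP 10.3 and the table shells:

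- Title the tables *serious ADRs*, *ADRs*, *AEs with fatal outcome* and *AESIs*. The AESI table is already planned.
- Keep the treatment-emergent window (start of treatment to 28 days after the last dose) as a timing rule for all of them. It applies equally well to the collected events.
- Present causality only for fatal AEs and AESIs.
- Report no overall SAE or treatment-emergent AE incidence.
- Add a footnote: *Unrelated events that were neither fatal nor AESIs were not collected; percentages are not overall AE or SAE incidences and are not comparable with studies that collected all AEs.*

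The cost is SAP wording and shells. It needs no new data and leaves the efficacy analyses untouched.
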